4. SELECTION AND ENROLLMENT OF PARTICIPANTS

4.1 Inclusion Criteria

Participants must meet all of the inclusion criteria to participate in this study.

Randomized Control Trial

	Inclusion Criteria
1.	≥18 years of age
2.	Ability to communicate in English
3.	Level 3, 4, 5 on triage rate scale
4.	Acute musculoskeletal, back, pelvic, non-cardiac chest, abdominal, and headache pain (≥4 on the NRS) due to non-penetrating injury.

Qualitative Interviews

	Inclusion Criteria
1.	ED providers (physicians, nurse practitioners, physician assistants, and registered nurses) and ED staff employed in the UH Cleveland Medical Center ED (site 1), the VUMC ED (site 2) and the Hillcrest UCSD (site 3) for at least one year including the study period.
2.	Acupuncturists who are employed or credentialed by one of the participating institutions to perform acupuncture in the emergency department as part of the study.
3.	ACUITY study staff from the three recruiting ACUITY sites (UH, VUMC, UCSD)
4.	Patients who received acupuncture as part of the RCT.
5.	Access to the internet and a smart phone, computer or tablet.

4.2 Exclusion Criteria

All candidates meeting any of the exclusion criteria at baseline will be excluded from study participation

Randomized Control Trial

	Exclusion Criteria
1.	Fever exceeding 100° F
2.	Presenting with a chief complaint of a psychological / psychiatric concern

3.	Presenting with chief complaint of Migraine
4.	Current Pregnancy
5.	Self-reported or documented opioid medication taken orally within 4 hours
6.	Presenting with chief complaint of Joint Dislocation
7.	Presenting with chief complaint of Bone Fracture
8.	Confirmed or suspected COVID-19

Qualitative Interviews

N/A

4.3 Study Enrollment Procedures

Recruitment Methods

Randomized Control Trial: When a patient arrives in the participating ED (UH Cleveland Medical Center ED (site 1), the Vanderbilt University Medical Center (VUMC) ED (site 2) and the Hillcrest University of California San Diego (UCSD) ED (site 3)), they will be triaged by the triage nurse per current ED procedures. Pending permission of site ED leadership, pre-treatment study flyers can be posted at triage, in waiting areas, or in treatment spaces to offer a passive introduction to the study. Within the triage unit, potential subjects will be identified flagged by nursing staff and/or a member of the research staff. Patients who rate pain four or greater on the 11-point NRS scale will be considered for the study. At that time, the Study Coordinator (SC) or the Research Assistant (RA) will verify the patient's initial eligibility (age, understanding of English language, presence of pain) using the EHR. If the patient is potentially eligible, the SC or RA, if able, will approach the patient while in the waiting room to be seen by their provider to hand them the patient recruitment flyer. The SC or RA will continue to monitor his or her status and location within the ED using the EHR. The patient will then be roomed and seen by the ED clinical provider. If the ED provider determines that patient does not have a clinical condition prohibiting study participation, s/he will sign a study approval form and give back to the SC or RA. Thereafter, the SC or RA will approach the potential subject to introduce the study. If the person is interested in study participation after they have been assigned to a room, the SC or RA will assess patient's capacity to understand and sign documentation, if patient is capable then they will seek to obtain informed consent. The consent will inform the patient that if they are randomized to receive acupuncture a study team member may contact them to ask if they would like to participate in an additional interview, and that they may refuse to participate in the interview portion of the study without affecting their participation in the other portion of the research. They will be informed that the interview will be recorded and transcribed and that a study information sheet will be shared and reviewed with them prior to the start of the interview. If the patient is not interested in participating in the study or refuses to provide their phone number and email for follow up assessments, a reason for refusal will be documented by the SC or RA in our computerized study database.

Individuals who participate in the ED data collection procedures will be remunerated \$25 and those who complete the 1-week and 4-week follow-up assessments will be remunerated an additional \$25 per visit. Remuneration will happen within 45 days of the patients' ED stay. There is no current plan for recruitment or advertisement materials due to the nature of this study and immediate recruitment of subjects.

Qualitative Interviews:

Patient Interview Recruitment Methods: Patients who participate in the RCT will have been informed as part of the informed consent process that they may be contacted to participate in a qualitative interview if they are assigned to the acupuncture group, and they will have been given the option to opt out of being contacted for the interview. Study staff from the Einstein Coordinating Center, who will be

research credentialed, will contact the patients in the acupuncture group via email and/or phone within a week of their ED visit to schedule the interview and to share the study information sheet for them to review. Participant contact with the research staff for qualitative interviews will be documented in REDCap with up to 5 attempts to schedule the qualitative interview.

ACUITY Study Staff Interview Recruitment Methods will be scheduled to occur either in person in a private room, when possible, or remotely via a HIPAA-compliant commercial tele-health platform: (e.g. Zoom Health Professional or Doxy.me) by research credentialed study staff from Einstein Coordinating Center. Study staff will have the choice of audio or video interview. Einstein Coordinating Center staff conducting the interviews remotely will be in a private room when interviewing the participants. A stamped copy of the informed consent document will be shared with the participant before the scheduled informed consent process, and the consent will be signed and dated by the participant and by the Einstein staff conducting the informed consent process, either in person or electronically using UH REDCap, before beginning the interview. The interviews will take approximately 45 minutes to complete and will be recorded and transcribed. A short demographics survey will be securely emailed to the participant during the interview via [contact] email address and will be completed and emailed back before the conclusion of the interview.

Provider Interview Recruitment Methods: We will use staff rosters to identify physicians, nurse practitioners, physician assistants, nurses and ED staff who have been employed by in the ED at one of the three sites during the data collection period and to identify ACUITY study staff and the acupuncturists performing the intervention as part of the study. Research Credentialed study staff from the Einstein Coordinating Center or local study staff who have been trained to conduct the qualitative interviews will contact these providers and staff, whether in person, or by email, followed by phone, to invite them to participate and to share study information sheet for them to review.

All individuals who participate in the qualitative interviews will be remunerated \$25 within 30 days of the interview. The qualitative interview team from Einstein Coordinating Center will inform respective site study staff once a patient's qualitative interview is complete. Site study staff will contact the patient with the e-gift card code or mail a physical gift card and will mark in REDCap when this was completed.

Documentation of reasons for ineligibility.

We will maintain a screening and enrollment log to document ineligibility reasons and for non-participation of eligible candidates.

Consent Process

Randomized Control Trial Consent Process

The consent process will occur after the patient has gone through the triage process and been assigned to a room within the ED. The consent process will be conducted by dedicated research staff (SC or RA) that have been trained in obtaining informed consent. The status and location of the patient will be monitored by research staff using the EHR to ensure the patient is approached at an appropriate time.

All potential participants will be examined by an ED provider to ensure they do not need emergent care and have sufficient mental capacity to participate in the study. If the ED provider determines that patient does not have a clinical condition prohibiting study participation, s/he will sign a study approval form. Research staff will assess patient capacity to understand and sign study documentation prior to obtaining consent. If patient is capable to continue, research staff (SC or RA) will consent potential participants. In doing so, they will explain the study, including benefits, risks and interventions. The research staff will stress to the patient that participation is voluntary and they may withdraw from the study at any time. Consent decline or withdrawal from the study will not affect the patient's continued care in the ED. As per other studies conducted by the PI, the research staff will be trained to answer all questions that may arise. Privacy will be ensured by conducting all study related interactions, including the consent process, within the patient's private ED treatment room. Patients will be provided ample

time to go through the consent process and ask any questions. Time for decision making will be minimized due to the fast-paced and urgent nature of the ED. After a member of the research staff explains the consent form, study requirements and answers all of the patient's questions about the study, patients will provide written consent. Only the participating patients themselves will be allowed to provide consent for inclusion into the study. No legally authorized representative (LAR) may enroll a patient into the study. Study activity may only continue after the patient has provided written consent. If a patient declines to participate or is unable to sign the consent document, a reason for refusal will be asked and documented in the study database. It will be considered a declination of participation if a patient refuses to provide study staff with their phone number and email address during the baseline assessment. Patients who decline participation will not be allowed to opt into the study for the remainder of that particular ED visit. However, they would be eligible to participate at a future ED visit if interested and if the study is still in the recruitment phase. If a patient enrolls in the study, he or she will no longer be eligible for study participation during future ED visits within the recruitment period. We will utilize the EHR, and the 21 CFR Part 11 compliant data collection tool (e.g., REDCap), to verify the patient has not previously participated in the study.

Qualitative Interviews Consent Processes

Patient Interview Consent Process: Patients who are consented to participate in the RCT will be informed as part of that consent process that if they are randomized to receive acupuncture as part of the study, we may approach them to invite them to participate in an interview. The consent form will include language informing the patient that the interview will take place via the audio-only function of a HIPAA-compliant commercial tele-health platform: (e.g. Zoom Health Professional or Doxy.me) and will be recorded and transcribed. There will also be an option for the participant to opt out of being contacted for the interview. Research credentialed study staff at the Einstein Coordinating Center will contact participants randomized to the acupuncture arm within a week after their ED visit to schedule the interview and to share the study information sheet to review. Participant contact with the research staff for qualitative interviews will be documented in REDCap with up to 5 attempts to schedule the qualitative interview. At the time of the interview, the interviewer will review the study information sheet with the patient. This document will explain that the interview will be recorded and transcribed, and will reiterate the voluntariness of participation. The document will explain that if the participant continues with the interview, they are agreeing that they have read the information and that they voluntarily agree to participate and to be recorded for transcription purposes.

Provider Interview Consent Process: Identified providers/staff and study staff will be contacted by research credentialed study staff at The Einstein Coordinating Center, either in person during their site visit or via email followed by phone, and invited to participate in the interview. They will schedule the interview at the providers' convenience. A study information sheet will be shared via email with the provider ahead of the interview, and will be reviewed at the beginning of the scheduled interview. This document will explain that the interview will be recorded and transcribed, and will reiterate the voluntariness of participation. The document will explain that if the participant continues with the interview, they are agreeing that they have read the information and that they voluntarily agree to participate and to be recorded and transcribed.

The research staff conducting the informed consent process will introduce the study as an investigation to describe perspectives and experiences related to implementation of the acupuncture study in the ED. The study information sheet will be reviewed with each participant, and participants will be encouraged to ask questions throughout the process. Research staff will stress the points that this is a voluntary study, and that a participant is able to refuse to take part in any part of the study or to withdraw from the study at any time, without any impact on their care or on their employment/consulting privileges at the sites. Consent to be interviewed and for the interview to be recorded will be obtained verbally. Only individuals able to consent of their own volition will be enrolled.

ACUITY Study Staff Interview Consent Process: Research credentialed study staff at The Einstein Coordinating Center will contact identified ACUITY study staff by email followed by telephone and invite them to participate in the interview. If the staff member agrees to participate, the Einstein staff member will email a copy of the stamped consent form to review ahead of the scheduled informed consent process and interview. The informed consent process and interview will take place either in person in a private room when possible, or remotely via a HIPAA-compliant commercial tele-health platform. The written informed consent process will be captured in UH REDCap when done remotely. The research staff conducting the informed consent process will introduce the study as an investigation to describe perspectives and experiences related to implementation of the acupuncture study. The informed consent document will be reviewed with each participant, and participants will be encouraged to ask questions throughout the process. This informed consent document will explain that the interview will be recorded and transcribed, and will reiterate the voluntariness of participation.

Einstein staff will stress the points that this is a voluntary study, and that a participant is able to refuse to take part in any part of the study or to withdraw from the study at any time, without any impact on their care or on their student standing, employment or consulting privileges at the sites. Only individuals able to consent of their own volition will be enrolled.

Structured Observations Consent Process:

Observations of screening and recruitment will be conducted by UH Research Credentialed study staff. The study coordinator or research assistant who recruit patients in the ED will introduce the additional study staff and explain that they are observing the interactions and taking notes. They will be given the opportunity to verbally refuse to be observed during consent. The consent form will also have an option to opt out of further observation of study procedures. Study staff in the ED, including the acupuncturists, will provide written consent ahead of time to be observed during the observation site visit.

Provider Feasibility Survey Consent Process:

We will use staff rosters to identify physicians, nurse practitioners, physician assistants, nurses and ED staff who have been employed by in the ED at one of the three sites during the data collection period. A recruitment email will be set via REDCap to invite participation. Providers and staff who are interested will click a link to the feasibility study information sheet. Those who wish to participate will click “yes” and be directed to the survey. Up to 4 reminder emails will be sent.

We will also distribute a recruitment flyer in the ED at each site, inviting ED providers and staff to participate. The flyer will include a QR code that links directly to the study information sheet. Those who wish to participate will click “yes” and be directed to the survey. A \$5 incentive will be provided to participants who complete the feasibility survey. Contact information to send the incentive will be collected in a separate REDCap form from the survey to maintain confidentiality.

Randomization

Random assignments will be made by the study statistician in permuted blocks of size 2 and 4. The block size will also be randomly generated to minimize correct prediction of assignments and preserve approximate balance between groups, using the rand function in SAS. The randomization module will be built into REDCap. Study staff (SC or RA) will enable randomization in REDCap for each participant after completion of the informed consent process and baseline data collection. If the REDCap randomization module is not available, envelopes will be used. Personnel from the Albert Einstein School of Medicine will prepare each randomization packet in a sealed envelope and send these to each site in batches. A date/signature label will be placed over the envelope seal. Randomization envelopes will be stored in locked cabinets and opened by study staff (SC or RA) after completion of the informed consent process and baseline data collection.

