The objectives of this study are to: conduct a feasibility randomized control trial (RCT), to examine the feasibility of data collection in the RCT, develop a responsive acupuncture intervention and assess implementation and treatment outcomes in emergency departments associated with 3 BraveNet research sites. (UH Cleveland Medical Center ED (site 1), the Vanderbilt University Medical Center (VUMC) ED (site 2) and the Hillcrest University of California San Diego (UCSD) ED (site 3)). This study will include qualitative interviews and structured observation to assess feasibility of implementation.

Design and Outcomes

This is a multi-site single visit, un-blinded, feasibility randomized control trial of acupuncture in the ED.

Interventions and Duration

Acupuncture for pain management in the Emergency Department (ED) will be compared to usual care. The interventions will be administered during the ED visit. During that time, pre-, post- and discharge assessments will be administered. Follow up assessments will take place at one and four weeks post ED visit.

Sample Size and Population

The target population are adults presenting to the ED with acute non-emergent (musculoskeletal, back, pelvic, non-cardiac chest, abdominal, flank or head) pain ≥ 4 on a 0-10-point Numeric Rating Scale (NRS) due to non-penetrating injury. A total of 150 patients (50 patients per recruiting site) plus 15 pilot (5 per recruiting site) will be recruited study-wide.

Additionally, 30 (10/site) ED stakeholders, including providers (physicians, nurse practitioners, physician assistants, and registered nurses) and ED staff employed for at least one year including the study period, as well as acupuncturists who are employed or credentialed by one of the participating institutions to perform acupuncture in the emergency department as part of the study will be interviewed about their perspectives and experiences related to implementation of the acupuncture study in the ED.

Patients who are randomized to the acupuncture group will be contacted to participate in a brief qualitative interview about 3 weeks after their ED visit. The expectation is that up to 15 patient participants per site (n=45 total) will consent to the qualitative interviews about their experience of receiving acupuncture as part of the RCT.

STUDY OBJECTIVES

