6.2 Description of Evaluations

6.2.1 Screening Evaluation

At each ED, the Study Coordinator (SC) or Research Assistant (SC) and acupuncturist will work as a team, staffing an average 2.5, 4-6 hour recruitment/intervention sessions per week, varying the times

and days across sites as this may influence adoption. As in Figure 1, after the ED RN conducts the initial triage activity, the SC or RA (“study staff”) will identify and conduct initial eligibility pre-screening in the in the ED triage unit. The patient will then be roomed and seen by the ED clinical provider. If the ED provider determines that patient does not have a clinical condition prohibiting study participation, s/he will sign a study approval form (see below). The study staff will then approach the patient for study participation.

Provider sign off

Acupuncture in the Emergency Department for Pain Management (ACUITY)

If the patient is randomized to the acupuncture arm, please withhold pain and anxiety medications until after the acupuncture session.

The study coordinator will inform you what arm they are assigned to and when their session has ended.

In order for this patient to be eligible to participate in the "Acupuncture in the ED" study, please verify you have examined the patient and believe to the best of your knowledge, at this time, that the patient does not have the following conditions:

Critical status / Trauma
 Bone fracture
 Joint dislocation
 Migraine
 Psychological / psychiatric concern
 Clinical judgement / Other:

If you deem the patient eligible for the study, the patient will be randomized to acupuncture or usual care.

Patient can continue in study
 Patient is excluded from study

Sign: _____

Consenting Procedure

We have requested a partial HIPAA waiver for prescreening. Therefore, patients will only be consented once the screening process is over and eligibility is confirmed.

The consent process will occur after the patient has gone through the triage process and been assigned to a room within the ED. The consent process will be conducted by dedicated research staff (SC or RA) that have been trained in obtaining informed consent and who have current Human Subjects Protection and Good Clinical Practice certifications. The status and location of the patient will be monitored by

research staff using the EHR to ensure the patient is approached at an appropriate time.

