6.2.3 Blinding

Data collectors in the ED will be masked to study outcomes of a given patient by use of electronic data collection methods.

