10.3 Quality Assurance

10.3.1 Training

The site Study Coordinator (SC) will ensure that all study personnel have completed all required

institution-specific and protocol-specific trainings and that these trainings are documented appropriately on the Training Log. The SC will also ensure that new personnel are appropriately documented on the Delegation of Responsibilities Log (DOR). While training should be completed and documented in real time, the Multi-Site Study Coordinator (MSC) will verify that all training is current and appropriately documented on a quarterly basis, as noted in section 10.3.2 below.

Institution-specific Training

All study staff will complete CITI or NIH Human Subjects training prior to commencement of study activities. The site staff is also required to receive Good Clinical Practice (GCP) training through CITI or the Society for Behavioral Health. Staff training certificates will be stored in the Regulatory Binder in REDCap and documented on the Training Log.

Protocol-specific Training

Below is a summary of required initial training by role for new study personnel.

PI, Study Coordinators, Research Assistants and anyone recruiting patients:

- ✓ Review and express understanding of the Site Initiation Visit (SIV) training slides
- ✓ Review and express understanding of the IRB protocol
- ✓ Review and express understanding of the NCCIH protocol
- ✓ Review and express understanding of the Informed Consents and Study Information Sheets
- ✓ Review and express understanding of the MOP

ED Physician and Students who are not recruiting patients:

- ✓ Review and express understanding of the IRB protocol
- ✓ Review and express understanding of the Informed Consents and Study Information Sheets

Statistician

- ✓ Review and express understanding of the IRB protocol

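### The protocol that recruiters must read prints the block sizes (2 and 4) of an open-label trial, which undercuts its own aim of limiting prediction of the next assignment

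*Combined protocol and SAP*

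**What the plan says.** Section 4.3 (Randomization) specifies: "Random assignments will be made by the study statistician in permuted blocks of size 2 and 4". It adds: "The block size will also be randomly generated to minimize correct prediction of assignments and preserve approximate balance between groups". The same two sizes are given in Section 3 (Randomization) and Section 9.2 (Treatment Assignment Procedures).

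Section 10.3.1 lists required training for "PI, Study Coordinators, Research Assistants and anyone recruiting patients". The first protocol-related item after the site initiation slides is: "Review and express understanding of the IRB protocol". The NCCIH protocol is also on the list. No section tells anyone to keep block sizes from these staff.

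The Précis describes the design: "This is a multi-site single visit, un-blinded, feasibility randomized control trial of acupuncture in the ED". Section 6.2.3 masks scores, not arms: "Data collectors in the ED will be masked to study outcomes of a given patient by use of electronic data collection methods". The provider sign-off form in Section 6.2.1 shows that recruiting staff learn the arm: "The study coordinator will inform you what arm they are assigned to and when their session has ended". On consent, Section 4.3 says: "The consent process will be conducted by dedicated research staff (SC or RA) that have been trained in obtaining informed consent". The same section has the coordinator or assistant approach the patient and trigger randomisation.

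The sections differ on mechanism. Sections 3 and 9.2 describe sealed envelopes sent to each site. Section 4.3 describes a REDCap module, with envelopes to each site as back-up. None says whether the REDCap list is stratified by site, or how likely each block size is.

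**The concern.** Opening the assignment only after consent and baseline conceals the current slot. It does not stop a recruiter from inferring the next slot from past assignments before deciding whether and when to approach the next patient. Randomly varying the block size is meant to prevent that inference, but it protects less when the possible sizes are only 2 and 4 and are printed in a document the recruiter must study.

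Foresight could matter here. Recruiters have some discretion over timing, they work in sessions paired with an acupuncturist (Section 6.2.1), and the arms differ in when pain medication is given (Section 5.3.3). Recruitment and retention are the primary outcomes (Section 3) and are to be examined by patient group and by arm (Section 9.5.1). Selective approach could therefore distort who is enrolled in each arm. The primary objective is to refine procedures for a later full trial (Section 1.1), so a weakness left in the randomisation could carry forward.

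**Working it through.** The plan gives no predictability figure, so there is nothing to reproduce.

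**Inputs from the documents:** block sizes 2 and 4 in random order (Section 4.3); 50 patients at each of three sites, 150 in all (Section 9.2); 1:1 allocation, implied by blocks of 2.

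**Assumptions the documents do not state:** (a) the two sizes are equally likely; (b) each site has its own list; (c) the recruiter knows all earlier assignments on that list.

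**Share of assignments that are certain.** An observer who knows the sizes but not the current block's size can be certain only when the running imbalance reaches 2. That needs a 4-block opening with two of the same arm. Of the 6 arrangements of a 4-block, 2 do so (probability 1/3), and the next two assignments are then forced. Let p be the probability that a block has size 4.

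- Certain assignments per block: p × 1/3 × 2
- Mean block length: 2(1 − p) + 4p = 2(1 + p)
- Long-run certain share: p / [3(1 + p)]

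At p = 1/2 this is (1/2 × 1/3 × 2) / 3 = 1/9, or 11.1%. An exact recursion for a list of 50 gives 5.41 certain assignments, or 10.8%. Over three lists that is 3 × 5.41 = 16.2, about 16 of 150.

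**Varying assumption (a):**

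| p | Certain share |
|---|---|
| 1/4 | 0.25/3.75 = 1 in 15 |
| 1/3 | 1 in 12 |
| 1/2 | 1 in 9 |
| 2/3 | 1 in 7.5 |
| 3/4 | 0.75/5.25 = 1 in 7 |

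**Best guess and alternative blocks.** Simulated lists of 50, equally likely sizes, with an observer who updates by Bayes' rule on all earlier assignments:

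| Block sizes | Certain | Best guess correct |
|---|---|---|
| 2, 4 | about 10.8% (16 of 150) | 72% |
| 4, 6 | about 5.7% (8 to 9 of 150) | 69% |
| 4, 6, 8 | about 2.4% (about 4 of 150) | 68% |

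Chance is 50%.

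**Relaxing assumptions (b) and (c), blocks of 2 and 4:**

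- The recruiter sees a random half of a site list and is still granted the list position: about 1.4% certain (about 2 of 150), best guess about 60%.
- One list of 150 is shared by three sites enrolling at random, the recruiter sees only one site's third, and list position is again granted: about 0.4% certain, best guess about 57%.
- Same shared list, with the simple rule of guessing against a site imbalance of 2 or more: right about 52% of the time.

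**The case against.** A reader might infer that about one in nine assignments in this trial can be known in advance. The documents do not support that as a statement of fact, because it needs all three assumptions above. Only the envelopes are described as going to each site, and under Section 4.3 they are the back-up. Nothing shows that one recruiter sees every assignment. The work is shared between coordinator and assistant, and follow-up calls must be made by someone who did not meet the patient in the ED (Sections 6.2.4 and 6.2.5), so more than one person is expected. Staff could pool what they know, but that too is an assumption. This objection stands, and the figure is given here only conditionally.

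A reader might also infer that enrolment will be biased. The documents show no manipulation, and predictability is not bias. Safeguards exist: block size varies at random, assignment follows consent and baseline, nursing staff may flag patients, and an ED provider must sign off before the approach (Sections 4.3 and 6.2.1). Non-participation is logged (Section 4.3), and demographics and complaint are collected for all eligible patients (Section 9.5.1), so selection on those features could be examined. Pain outcomes are summarised descriptively (Section 9.5), and the non-inferiority test belongs to the future trial (Section 9.2). These points limit the importance. They do not justify printing the sizes for recruiters.

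Finally, small blocks buy close balance in lists of 50, which is a legitimate aim. That supports a modest increase in size, not abandoning blocking.

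**Conclusion.** The concern holds in a limited form. Disclosing blocks of 2 and 4 to recruiters in an open-label trial weakens the plan's own protection against prediction. The size of the weakness depends on facts the documents leave out. With site lists, equally likely sizes and full knowledge of the site's history, about 11% of assignments would be certain and the best guess would be right 72% of the time. If 4-blocks have probability 1/4 to 3/4, the certain share runs from 1 in 15 to 1 in 7. With partial knowledge or one shared list it is nearer 1% or below. No resulting bias has been quantified. This is a cheap improvement of small importance, not a flaw that threatens the trial's feasibility aims.

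**What to change.** 1. Delete the block sizes from Sections 3, 4.3 and 9.2 and keep them in a document held only by the statistician. It is enough for the protocol to say that randomly varying permuted blocks are used.
2. For lists not yet issued, drop blocks of 2 in favour of larger randomly mixed blocks, for example 4 and 6, or 4, 6 and 8.
3. State whether the list is separate for each site, and reconcile the envelope and REDCap descriptions. If REDCap now runs one shared list, do not move to site lists without the larger, undisclosed blocks. Site lists with 4, 6 and 8 (2.4% certain, 68% best guess) would be more predictable than the shared list modelled above (0.4%, 57%).

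**Gain:** modest. Under the site-list assumptions, certain assignments fall from about 16 to about 4 of 150 and the best guess from 72% to 68% with 4, 6 and 8. Withholding the sizes adds protection that these figures do not count, since they assume an observer who knows them.

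**Cost:** regenerating lists, editing three sections and slightly looser balance. At 50 per site the final imbalance can reach 4 with 4, 6 and 8 (an 8-block cut after four of the same arm), against 2 now. With 4 and 6 it stays at 2 at exactly 50, because the list stops after an even number of places in its last block. Sample size, visits and treatment are unchanged.
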